Revision 1 10/27/2021	Protocol was modified slightly in response to IRB critiques (clarifying 4-months is the window to report pregnancy after last dose); clarification that research samples for the correlatives will be collected under a biospecimen sample collection protocol. New protocol version date, 27OCT2021. This revised protocol also contains a new pill diary for Cabozantinib (new Appendix B); added clinicaltrials.gov identifier (cover page); clarifications re: urinalysis and aPTT tests (addresses questions re: Medicare coverage analysis). Resolution: Revision 1 protocol approved by IRB (11/23/2021).
12/22/2021	Open to Accrual
Amendment 1 04AUG2022	The protocol version date 27OCT2021 was modified to create Amendment 1, version dated 04AUG2022. Protocol edits are as follows: clarify 3.2.26 exclusion re: cavitating pulmonary lesions; clarify 3.2.27 exclusion criterion, invading blood vessels and encasement; and, clarify window for ECOG PS as within 2 weeks (sections 3.1.4, 4.3.3). Other minor updates in this amendment: trial opening date date trial (added above); noted the IND exemption from the FDA (page 1); text added to clarify language regarding emerging new first-line therapies (Schema); noted radiologist, affiliation address for imaging RECIST reads (Pg 1, 12.2.2, and 12.2.3).
Amendment 2 27MAR2023	The 04AUG2022 protocol was revised to correct the reporting of concomitant medications (S11 Study Calendar was clarified to align with Section 8.1). The Key Personnel (cover page) was updated. New protocol version date is 27MAR2023.
	Placeholder for future amendment
	Placeholder for future amendment

SCHEMA

NOTE: “1st line therapy” is defined as FOLFIRINOX and/or gemcitabine+abraxane, as well as other treatment regimens that are approved for 1st line therapy of metastatic pancreatic cancer during the course of this trial.

*One cycle of therapy is Q3W administration of pembrolizumab (200 mg IV) and cabozantinib (40 mg po daily).

*Completion of pembrolizumab Q3W monotherapy consists of 35 treatments (approximately 2 years). Discontinuation of treatment may be considered for participants who have attained a confirmed complete response (CR) and have been treated for at least 8 cycles (at least 24 weeks), receiving at least 2 cycles of the combination including 2 doses of pembrolizumab and at least 80% of the planned doses of cabozantinib beyond the date when the initial CR was declared.

TABLE OF CONTENTS

1.	OBJECTIVES	6

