- Serious non-healing wound/ulcer/bone fracture.
- Uncompensated/symptomatic hypothyroidism

3.2.29 Moderate to severe hepatic impairment (Child-Pugh B or C).

3.2.30 Is currently participating in or has participated in a study of an investigational agent or has used an investigational device within 4 weeks prior to the first dose of study intervention. Participants who have entered the follow-up phase of an investigational study may participate as long as it has been 4 weeks after the last dose of the previous investigational agent.

3.2.31 Has a history of (non-infectious) pneumonitis/interstitial lung disease that required steroids or has current pneumonitis/interstitial lung disease.

3.2.32 Has an active infection requiring systemic therapy.

3.2.33 Has a known history of Human Immunodeficiency Virus (HIV) infection. No HIV testing is required unless mandated by local health authority.

3.2.34 Has a known history of Hepatitis B (defined as Hepatitis B surface antigen [HBsAg] reactive) or known active Hepatitis C virus (defined as HCV RNA [qualitative] is detected) infection.

3.2.35 Has a known history of active TB (Bacillus Tuberculosis).

3.2.36 Has a history or current evidence of any condition, therapy, or laboratory abnormality that might confound the results of the study, interfere with the subject's participation for the full duration of the study, or is not in the best interest of the subject to participate, in the opinion of the treating investigator.

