6.1.3 Treatment Regimen

Table 2. Overview of Cabozantinib and Pembrolizumab Combination

Regimen Description					
Agent	Premedications; Precautions	Dose	Route	Schedule	Cycle Length
Pembrolizumab (MK-3475)	N/A	200 mg	IV infusion	Day 1, Q3 weeks	
Cabozantinib (XL184)	1 hour before or 2 hours after meal; take dose with 8oz water (minimum). Swallow tablets (do not crush or chew). Avoid grapefruit and Seville oranges during treatment.	40 mg	Oral	Daily	Q3 weeks
Notes:					

Cabozantinib: Subjects are to be instructed to not make up vomited doses and to maintain the planned dosing schedule. Subjects are not to make up for missed doses if more than 12 hours have elapsed after the time the subject would usually take Cabozantinib. In the event of missed doses, subjects are not to take 2 doses to make up for the one the subject missed.
 
Participants will be provided a daily dosing diary with instructions to record Cabozantinib, in accordance with the SOP on compliance with oral medications per Markey Cancer Center Quality Assurance Office.
 
 - The patient will be requested to maintain a medication diary of each dose of medication. - The diary will be distributed on C1D1 and collected at the beginning of Cycle 2, etc. - The medication diary will be returned to clinic staff at the end of each 21-day course. - The daily diary is not a CRF. The diary will serve as source documentation and be maintained with other subject clinical source documents. - Study staff should carefully review the diary with the subject and to ensure it is complete and accurate before transcription to the subject's CRFs. 					

Pembrolizumab Infusion Requirements and Guidance	
First Infusion	Subsequent Infusions:

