7.2 Cabozantinib

7.2.1 Product Description and Administration

Exelixis (one of the two co-sponsors) will provide adequate supplies of Cabozantinib, which will be supplied as 40-mg yellow film-coated tablets and also as 20-mg yellow film-coated tablets.

The components of the tablets are listed below.

40 mg Cabozantinib tablets are yellow film-coated, oval shaped with no score, and debossed with "XL" on one side and "60" on the other side.

20 mg CABOMETYX tablets are yellow film-coated, round with no score, and debossed with "XL" on one side and "20" on the other side.

Table 3. Cabozantinib Tablet Components and Composition

Ingredient	Function	% w/w ^a
Cabozantinib Drug Substance (25% drug load as free base)	Active Ingredient	31.68
Microcrystalline Cellulose (Avicel® PH-102)	Filler	38.85
Lactose Anhydrous (60M)	Filler	19.42
Hydroxypropyl Cellulose (EXF)	Binder	3.00
Croscarmellose Sodium (Ac-Di-Sol®)	Disintegrant	6.00
Colloidal Silicon Dioxide	Glidant	0.30
Magnesium Stearate	Lubricant	0.75
Opadry® yellow film coating which includes HPMC 2910/hypromellose 6 cp, titanium dioxide, triacetin, and iron oxide yellow	Film Coating	4.00

^a weight fraction, expressed in percentage; HPMC, Hydroxypropyl methylcellulose

Preparation, Storage and Stability

Store at 20°C to 25°C (68°F to 77°F); excursions permitted from 15°C to 30°C (59°F to 86°F).

Administration

Refer to the treatment section for specific administration instructions. Oral: 40 mg once daily, continue as long as benefiting clinically or until unacceptable toxicity (Choueiri 2021); do not exceed 60 mg daily. Administer on an empty stomach (1 hour before or 2 hours after eating).

Note: The prescribing information (for Cometriq) describes when to give food with respect to Cabozantinib; no food should be consumed for at least 2 hours before or for at least 1 hour after the Cabozantinib dose. Swallow whole; do not crush tablets. Do not substitute Cabozantinib tablets.

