7.2.3 Management of Adverse Reactions from Cabozantinib

Withhold CABOZANTINIB for NCI CTCAE Grade 4 adverse reactions, and for Grade 3 or intolerable Grade 2 adverse reactions that cannot be managed with a dose reduction or supportive care.

Upon resolution/improvement (i.e., return to baseline or resolution to Grade 1) of an adverse reaction, reduce the dose as follows:

- If previously receiving 60 mg daily dose, resume treatment at 40 mg daily
- If previously receiving 40 mg daily dose, resume treatment at 20 mg daily
- If previously receiving 20 mg daily dose, resume at 20 mg if tolerated, otherwise, discontinue CABOZANTINIB

Permanently discontinue CABOZANTINIB for any of the following:

- development of unmanageable fistula or GI perforation
- severe hemorrhage
- arterial thromboembolic event (e.g., myocardial infarction, cerebral infarction)
- hypertensive crisis or severe hypertension despite optimal medical management
- nephrotic syndrome
- reversible posterior leukoencephalopathy syndrome

In Patients Concurrently Taking a Strong CYP3A4 Inhibitor: Reduce the daily CABOZANTINIB dose by 20 mg (for example, from 40 mg to 20 mg daily). Resume the dose that was used prior to initiating the CYP3A4 inhibitor 2 to 3 days after discontinuation of the strong inhibitor

In Patients Concurrently Taking a Strong CYP3A4 Inducer: Increase the daily CABOZANTINIB dose by 20 mg (for example, from 40 mg to 60 mg daily or from 20 mg to 40 mg daily) as tolerated. Resume the dose that was used prior to initiating the CYP3A4 inducer 2 to 3 days after discontinuation of the strong inducer. The daily dose of CABOZANTINIB should not exceed 80 mg.

In Patients with Hepatic Impairment: Reduce the starting dose of CABOZANTINIB to 20 mg once daily in patients with mild or moderate hepatic impairment. CABOZANTINIB is not recommended for use in patients with severe hepatic impairment.

Nursing Guidelines

Monitor vital signs prior to infusion, then every 15 minutes until 1 hour after infusion on first dose.

All patients with a history of infusion reactions to this immunotherapy should be monitored every 15 minutes until 1 hour after the end of the infusion.

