8. DOSING DELAYS/DOSE MODIFICATIONS

Study participants will be monitored for AEs from the time of signing consent through 100-days after the date of the decision to permanently discontinue all study treatment (i.e., last dose). Participants will be instructed to notify their physician immediately for any occurring AE.

The following should be taken into consideration in decisions regarding dose modifications (reductions and/or delays) for treatment-related side effects.

Cabozantinib and Pembrolizumab have class-specific safety profiles based on their mechanism of action but may also cause AEs that overlap. For management of AEs that can be clearly attributed to Cabozantinib or Pembrolizumab, independent dose modification for either agent is allowed.

- Examples of VEGFR TKI associated AEs caused by Cabozantinib are hypertension and hand-foot syndrome.
- Examples of irAEs and common AEs caused by Pembrolizumab are fatigue,

musculoskeletal pain, decreased appetite, pruritus, diarrhea, nausea, rash, pyrexia, cough, dyspnea, constipation, pain, and abdominal pain.

- Examples of overlapping AEs are diarrhea and elevations in liver function tests.

Table 5. Dose Modifications.

Dose Level	Cabozantinib Dose	Pembrolizumab Dose
0 (starting dose)	40 mg, oral, qd	200mg, IV, Q3weeks
-1	20 mg, oral, qd	200mg, IV, Q3weeks
-2	20 mg, oral, qod	200mg, IV, Q3weeks
-3	Discontinue Cabo	200mg, IV, Q3weeks

Other allowed dose interruption for pembrolizumab

Pembrolizumab may be interrupted for situations other than treatment-related AEs such as medical / surgical events or logistical reasons not related to study therapy. Participants should be placed back on study therapy within 3 weeks of the scheduled interruption, unless otherwise discussed with the Sponsor. The reason for interruption should be documented in the patient's study record.

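### Section 7.2.3 gives a different cabozantinib starting dose for mild or moderate hepatic impairment from the schema, Tables 2 and 5 and Section 7.2.1, and nothing says whether it is an exception

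*Combined protocol and SAP*

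**What the plan says.** Four places in the combined protocol and SAP give one cabozantinib dose without any hepatic condition:

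- Schema: "One cycle of therapy is Q3W administration of pembrolizumab (200 mg IV) and cabozantinib (40 mg po daily".
- Section 6.1.3, Table 2: 40 mg orally each day.
- Section 7.2.1: "Oral: 40 mg once daily, continue as long as benefiting clinically or until unacceptable toxicity".
- Section 8, Table 5: the row labelled "0 (starting dose") lists 40 mg once daily.

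Section 7.2.3, on managing adverse reactions, gives another starting dose for a subgroup: "Reduce the starting dose of CABOZANTINIB to 20 mg once daily in patients with mild or moderate hepatic impairment". It continues: "CABOZANTINIB is not recommended for use in patients with severe hepatic impairment".

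Two eligibility items bear on who that subgroup is. Exclusion 3.2.29 reads "Moderate to severe hepatic impairment (Child-Pugh B or C"). Inclusion criterion 3.1.5 allows AST/ALT up to 2.5 times the upper limit of normal (ULN), or 5 times with liver metastases. It allows total bilirubin up to 1.5 times ULN, or higher if direct bilirubin is within normal limits.

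**The concern.** A prescriber who works from the schema or either dosing table finds one starting dose and no sign that hepatic function matters. A prescriber who reaches 7.2.3 finds half that dose for a group that includes eligible patients. The protocol does not say which text governs when both apply, and it does not say how to recognise the group. The 7.2.3 rule also names a category that the eligibility criteria exclude, so it is unclear whether the paragraph was adapted to this trial.

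What is at stake is consistent dosing at the start of treatment, which is a patient-safety matter. It also affects how exposure can be described afterwards, because the protocol would not show whether a 20 mg start was planned or a deviation.

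**Working it through.** The protocol states no statistical figure on this point, so the check sets the passages side by side.

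**Step 1. Starting dose by location**

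| Place | Starting dose | Hepatic condition | Refers to 7.2.3? |
|---|---|---|---|
| Schema | 40 mg daily | none | no |
| 6.1.3, Table 2 | 40 mg daily | none | no |
| 7.2.1 | 40 mg daily | none | no |
| 8, Table 5, level 0 | 40 mg daily | none | no |
| 7.2.3 | 20 mg daily | mild or moderate impairment | – |

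Ratio of the two doses: 40/20 = 2.

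**Step 2. Which hepatic categories can be present at entry**

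- Severe: excluded by 3.2.29. The 7.2.3 sentence on severe impairment has no eligible patient to apply to at entry.
- Moderate: excluded by 3.2.29. That half of the 7.2.3 starting-dose rule also has no eligible patient to apply to at entry.
- Mild: not excluded. This is the only category in which the 7.2.3 rule can operate.

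**Step 3. Can mild be identified from the protocol?** Because 3.2.29 ties moderate and severe to Child-Pugh B and C, Child-Pugh A is implied for mild. It is nowhere stated. Neither the screening list in Section 4.3.3 nor the study calendar in Section 11 includes a Child-Pugh assessment. The limits in 3.1.5 let in patients with abnormal liver tests, but the protocol does not say whether such values alone count as mild impairment.

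**Step 4. Do the cross-references settle precedence?** Section 6.1 sends the reader to Section 7 for dose modifications, which favours 7.2.3. But 7.2.1 sends the reader back to the treatment section for administration, and Section 8, which is itself about dose modifications, names the starting dose in Table 5. No order of precedence is given.

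**Step 5. Is 7.2.3 otherwise consistent with the rest of the protocol?** Not fully. Besides naming an excluded category, it caps the daily dose at 80 mg when a strong CYP3A4 inducer is used, while Sections 7.2.1 and 8.2 give 60 mg as the maximum. The 60 mg step in its reduction list is weaker evidence, because the inducer rule can take a patient from 40 mg to 60 mg.

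**Step 6. After the start.** A patient who begins at 20 mg daily is already at Table 5 level -1. The next step differs: Table 5 goes to 20 mg every other day, while 7.2.3 resumes 20 mg if tolerated and otherwise discontinues. The protocol does not say how Table 5 applies to a patient who never received level 0.

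**Step 7. Sample size.** The calculation in Section 9.2 rests on median PFS of 2.0 and 4.0 months, one-sided 5% alpha, 80% power and an exponential distribution. None of these depends on the hepatic dosing rule.

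**The case against.** The strongest reply is that there is no conflict. To reduce a starting dose presupposes a general one. The schema, Tables 2 and 5 and Section 7.2.1 supply it, and 7.2.3 names the exception. None of the four general statements claims to hold whatever the hepatic function, and Section 6.1 points to Section 7. On this reading a patient with mild impairment has one starting dose. The reading is natural, and it may be what was meant. It is not secure, because Table 5 names a single starting dose, precedence is unstated, and 7.2.3 departs from the rest of the protocol on the excluded category and on the dose cap. It would also leave mild undefined.

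A second reply concerns practice. Recruitment is from the clinics of one cancer center (Section 4.3.1), and Section 7.1.1 requires standardized order sets approved by the research pharmacist. That stands as far as it goes: divergence between prescribers is less likely than it would be across many sites. The order set still has to be written from this protocol, and its content is not given.

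A third reply is that abnormal liver tests are not the same as hepatic impairment. This is correct. The limits in 3.1.5 show that patients with liver abnormalities can enrol; they do not show how many, if any, would be classed as mild.

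**Conclusion.** The inconsistency is real, and it is one of wording and cross-reference. The protocol contains two starting doses two-fold apart, does not say whether one is an exception to the other, and does not expressly define the only eligible group to which the second could apply. The number of patients affected cannot be derived from the documents and may be small. Sample size and power are unchanged.

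Three stronger inferences are not supported:

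- **That every eligible patient with mild impairment is definitely assigned two doses.** The exception reading is open, and no passage says that 40 mg applies to all.
- **That patients with moderate impairment are exposed to the conflict at entry.** They are excluded, so that wording is surplus.
- **That the PFS result becomes uninterpretable.** Table 5 already allows reduced dosing and discontinuation of cabozantinib, and Section 9.7.2 keeps patients with incorrect drug administration in the primary analysis. A few lower starting doses would add to variation in exposure that the design already accepts.

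The conclusion assumes that mild impairment is eligible because 3.2.29 does not name it, and that no order set or pharmacy document outside this protocol resolves the point.

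**What to change.** Reconcile the schema, exclusion 3.2.29, Table 2, Section 7.2.1, Section 7.2.3 and Table 5 on starting dose by hepatic function. In doing so:

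- state whether the 7.2.3 sentence is an exception to the general starting dose, and if it is kept, refer to it in the schema and both dosing tables;
- define the hepatic category once, and say whether the abnormal liver tests allowed by 3.1.5 fall within it;
- align the categories in 7.2.3 with 3.2.29;
- if two starting doses remain, say how the Table 5 levels and the 7.2.3 reduction steps apply to each.

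The choice of dose and rule belongs to the sponsor and investigators; none is proposed here. The cost is wording only, with a check that the order set matches. No endpoint, analysis or sample size needs to change.

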7.3 Pembrolizumab

Consult the package insert and investigator brochure for the most current and complete information.

7.3.1 Product description:

The recommended dose of KEYTRUDA in adults is 200 mg administered as an intravenous infusion over 30 minutes every 3 weeks until disease progression, unacceptable toxicity, or up to 24 months in patients without disease progression.

Investigational Product

The investigator shall take responsibility for and shall take all steps to maintain appropriate records and ensure appropriate supply, storage, handling, distribution and usage of investigational product in accordance with the protocol and any applicable laws and regulations.

Pembrolizumab will be provided by Merck as summarized in the table below.

Table 4. Product Description

Product Name & Potency	Dosage Form
Pembrolizumab 100 mg/ 4mL	Solution for Injection

Packaging and Labeling Information

Supplies will be labeled in accordance with regulatory requirements.

Clinical Supplies Disclosure

This trial is open-label; therefore, the participant, the trial site personnel, the Sponsor and/or designee are not blinded to treatment. Drug identity (name, strength) is included in the label text; random code/disclosure envelopes or lists are not provided.

Storage and Handling Requirements

Clinical supplies must be stored in a secure, limited-access location under the storage conditions specified on the label. Receipt and dispensing of trial medication must be recorded by an authorized person at the trial site. Clinical supplies may not be used for any purpose other than that stated in the protocol.

Returns and Reconciliation

The investigator is responsible for keeping accurate records of the clinical supplies received from Merck or designee, the amount dispensed to and returned by the participants and the amount remaining at the conclusion of the trial. Upon completion or termination of the study, all unused and/or partially used investigational product will be destroyed at the site per institutional policy. It is the Investigator's responsibility to arrange for disposal of all empty containers, provided that procedures for proper disposal have been established according to applicable federal, state, local and institutional guidelines and procedures, and provided that appropriate records of disposal are kept.

7.3.2 Dose modification and toxicity management for immune-related Adverse Events associated with pembrolizumab and combination therapy

AEs associated with pembrolizumab exposure, including coadministration with additional compounds, may represent an immunologic etiology. These immune-related AEs (irAEs) may occur shortly after the first dose or several months after the last dose of pembrolizumab/combination treatment and may affect more than one body system simultaneously. Therefore, early recognition and initiation of treatment is critical to reduce complications. Based on existing clinical study data, most irAEs were reversible and could be managed with interruptions of pembrolizumab/combination treatment, administration of corticosteroids, and/or other supportive care. For suspected irAEs, ensure adequate evaluation to confirm etiology or

exclude other causes. Additional procedures or tests such as bronchoscopy, endoscopy, or skin biopsy may be included as part of the evaluation. Based on the severity of irAEs, withhold or permanently discontinue pembrolizumab/combination treatment and administer corticosteroids.

Attribution of Toxicity:

When study interventions are administered in combination, attribution of an adverse event to a single component is likely to be difficult. Therefore, while the investigator may attribute a toxicity event [to the combination, to cabozantinib alone, or to pembrolizumab alone] for adverse events, both interventions must be held according to the criteria in section 8.

Holding Study Interventions:

When study interventions are administered in combination, if the AE is considered immune-related, both interventions should be held according to recommended dose modifications.

Restarting Study Interventions:

Participants may not have any dose modifications (no change in dose or schedule) of pembrolizumab in this study as described in Table 19.

- If the toxicity does not resolve or the criteria for resuming treatment are not met, the participant must be discontinued from all study interventions.
- If the toxicities do resolve and conditions are aligned with what is defined in [Table 19], the combination of cabozantinib and pembrolizumab may be restarted at the discretion of the investigator. In these cases where the toxicity is attributed to the combination or to cabozantinib alone, re-initiation of pembrolizumab as a monotherapy may be considered at the principal investigator's discretion.

7.3.3 Management of Adverse Reactions to Pembrolizumab dose holds or discontinuation Dose modification (Section 8) and toxicity management guidelines for irAEs in **Appendix F**.

